**provider/patient; instructor/student; supervisor/employee, etc.:**

- Having a 3rd person (family/friends, another study team member, etc.) present during the consent / assent discussion
- Having an independent advocate (e.g. advocate for decisionally impaired adults, wards) present during the consent / assent discussion
- Removing physical symbols of authority like white coats or police badges

**Sitting down beside the participant instead of standing over them**

- If obtaining consent / assent in a clinical setting, letting patients sit instead of lie down (if they are able to)

- Moving to a more neutral location like a conference room

- Obtaining consent / assent after other services/interactions have been completed (e.g. after school or the clinic visit)

**Having a mandatory wait period for the participant to go home and think before they sign consent /assent**

- Sharing the consent / assent discussion between two people (i.e. a clinician might be the best person to explain study procedures and risks, but then they could step out and let a research assistant finish the consent process)

- Other protection(s) not listed here – describe below

- N/A: Requesting Waiver of Consent

**9. \* Describe the other ways the study team will minimize any potential perception of undue influence to participate:**

Our team will offer enough privacy to let the Muslim women think and join to our study, our team is supported by the Mosque and our names and pictures will be on the Ads board to make sure we are trusted by the community.

**10. \* How much time will participants be given to make a decision:**

Two weeks after the first conversation about the study, we will drop the participant from out list if we have not heard back from her.

**11. If applicable, describe the procedures for consenting children upon entering adulthood or participants who are no longer decisionally impaired:**

# Consent Groups

1. \* Enter a descriptive name for this consent / assent group:  
Intervention group consent form

2. \* Select all that apply to this consent / assent group:

Name
 Signed Consent by Participant
 Signed Parent/Guardian Permission or Legally Authorized Representative Consent
 Signed Assent by Child or Decisionally Impaired Adult
 Verbal/Other Indication of Assent by Child or Decisionally Impaired Adult
 Short Form Consent (limited applicability)
 None of the Above (select waiver below)

3. \* Select all electronic signature platforms that apply to this consent / assent group:

 Not using electronic signature platforms
 DocuSign Part 11 (FDA regulated studies)
 DocuSign (standard platform for non-FDA regulated studies)
 REDCap e-Consent
 iMedConsent (Veterans Affairs studies)
 Other electronic signature platform

**4. If Other is selected, explain:****5. \* Select any waivers that apply to this consent / assent group:**

No Waivers Requested	
 Waiver of All Consent or Some Elements in Consent Form	
 Waiver of Parental Permission or Legally Authorized Representative Consent	
 Waiver of All Assent by Child or Decisionally Impaired Adult	
 Waiver of Signature on Consent/Permission Forms (waiver of documentation of consent)	
 Exception from Informed Consent (for emergency research only)	
6. * Select all study team role(s) that will obtain consent / assent from this group:	
Principal Investigator	
 Co/Sub-Investigator	
 Medical or Psychological Responsible Investigator	
Lead Student/Trainee Investigator (leading their own project)	
Research Coordinator	
 Research Nurse	
 Consultant	

Research Assistant	
Pharmacist	
Statistician	
Regulatory Coordinator	
Trainee/Student(working on project)	
Other	
N/A: Requesting Waiver of Consent	

**7. \* Describe the consent procedures used for this group. Address each point below:**

- When and where consent will occur
- What will be covered during the consent discussion
- How the consent discussion will occur (e.g. in-person, phone, video conference)
- How you will reconfirm consent on an ongoing basis, if applicable

**When and Where Consent Will Occur:**

Consent for the intervention group will be obtained at the Islamic Center during the scheduled education sessions. Participants will have the opportunity to provide consent before engaging in the educational program.

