The intervention group will consist of 20 participants who will receive one education session divided into three sections/videos. The session will be offered in a single day and last 1.5 hours. The session will include the following topics: 1) Risk of HPV infection (30 minutes), 2) Cervical cancer risk (30 minutes), and 3) Advantages and benefits of early screening and the HPV vaccine (30 minutes).

All participants from both groups will be given the survey at month 0 (baseline) after the delivery of the educational material. The survey will be self-report, available in both hard copy and electronic form with a QR code for Redcap.

Participants are expected to take approximately 45 minutes to complete the survey.

The Islamic center offer private room to practice the research activities in both phases ( Focus group and single arm trial)

**5. \* Does this study have a separate protocol document (i.e. a multisite or sponsor's protocol) that contains a detailed description of the study's methodology?**

Yes

No

**6. \* Since a separate protocol document is not uploaded, describe the proposed research using language understandable to those IRB committee members whose expertise is not scientific. The description must include:**

- 1. A statement explaining the study design**
- 2. A detailed description of all the procedures that will be followed to carry out the study, preferably in sequential order, and in sufficient detail that the study's methods could be replicated**
- 3. The schedule and frequency of when and how procedures will be conducted (e.g. in person, online, phone, paper, etc.)**
- 4. A description of all research measures/tests/interventions that will be used, including analyses/tests conducted on specimens/biological samples (if applicable)**

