**See the help text for additional guidance**

**1. A statement explaining the study design**

**Study Design:**

The proposed study consists of two parts.

Part 1 involves formative research through a focus group to gather insights and reach saturation.

Part 2 is a single-arm pre and post-test trial with the objective of evaluating the efficacy of an educational interventional program.

The study aims to increase cervical cancer screening (CC-S) and HPV vaccine (HPV-Vax) rates among Muslim American women (MAW) in Virginia, leading to a reduction in cervical cancer (CC) incidence and mortality.

2. A detailed description of all the procedures that will be followed to carry out the study, preferably in sequential order, and in sufficient detail that the study's methods could be replicated.
  - a. Part 1 - Formative Research: Conduct a focus group with 10 participants until saturation is reached.
  - b. Part 2 - Single-arm Pre and Post-test Trial: Enroll 20 participants to evaluate the educational program's effectiveness.

Participants will complete a baseline survey to assess their knowledge, attitudes, CC-S and HPV-Vax practices, and predisposing factors.

The survey will cover topics such as CC knowledge, experiences of medical mistrust, discrimination, spiritual coping, and fatalism.

3. The schedule and frequency of when and how procedures will be conducted (e.g. in person, online, phone, paper, etc.)

All procedures will be conducted in person at the Islamic Centers, except for follow-up phone calls.

Recruitment will occur during regular Friday prayers and religious holidays.

Participants will receive a brochure explaining the study and be screened for eligibility by the Research Assistant (RA). Eligible participants will be given a telephone contact for enrollment at a more convenient time.

The consent process will involve verbal explanation, providing the consent form in English, and allowing participants to ask questions. Follow-up surveys and confirmations will be conducted via phone calls.

4. A description of all research measures/tests/interventions that will be used, including analyses/tests conducted on specimens/biological samples (if applicable)

**Power Analysis:** No power analysis for this study. A target sample size of 20 participants has been determined based on PhD committee, the purpose of the project is training for the STUDENT.

Measures: Validated scales and surveys will be used to measure

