**How the Consent Discussion Will Occur:**

The consent discussion will occur in-person, allowing for direct communication between the research team and the participants. A designated research team member, such as the research assistant (RA), will conduct the discussion in a private room at the Islamic Center. The participant will have the opportunity to review the consent form, ask any questions, and discuss any concerns before making an informed decision to participate. The RA will be available to provide explanations and guidance as needed to ensure the participant's understanding of the study and their role in it.

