**How Consent Will Be Reconfirmed on an Ongoing Basis:**

Since the intervention group will be participating in a one-day educational program, ongoing reconfirmation of consent is not applicable in this case. However, the research team will ensure that participants are aware of their right to withdraw from the study at any time, even after providing initial consent. Participants will also be provided with contact information to reach out to the research team if they have any questions or concerns during or after the educational program.

**8. \* Select the processes for minimizing any potential perception of undue influence to participate, particularly when there is a pre-existing relationship between the participant and the researcher (e.g. treatment provider/patient, instructor/student, supervisor/employee, etc.):**

- Having a 3rd person (family/friends, another study team member, etc.) present during the consent / assent discussion
- Having an independent advocate (e.g. advocate for decisionally impaired adults, wards) present during the consent / assent discussion
- Removing physical symbols of authority like white coats or police badges
- Sitting down beside the participant instead of standing over them
- If obtaining consent / assent in a clinical setting, letting patients sit instead of lie down (if they are able to)
- Moving to a more neutral location like a conference room
- Obtaining consent / assent after other services/interactions have been completed (e.g. after school or the clinic visit)

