**Having a mandatory wait period for the participant to go home and think before they sign consent /assent**

- Sharing the consent / assent discussion between two people (i.e. a clinician might be the best person to explain study procedures and risks, but then they could step out and let a research assistant finish the consent process)
- Other protection(s) not listed here – describe below
- N/A: Requesting Waiver of Consent
- Other

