**10. \* How much time will participants be given to make a decision:**

Participants will be given sufficient time (expecting from a week to two weeks) to make a decision regarding their participation in the study. The exact duration may vary depending on the circumstances and complexity of the study. Typically, participants are encouraged to take as much time as they need to review the provided information, ask questions, and consider their decision.

The study team will emphasize that there is no rush to make a decision and that participants are free to take the necessary time to make an informed choice that aligns with their interests and preferences.

**11. If applicable, describe the procedures for consenting children upon entering adulthood or participants who are no longer decisionally impaired:**

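### As written, intervention-group consent is taken at the education session, which leaves no room for the go-home wait that the same form selects; no earlier consent discussion is described

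*Combined protocol and SAP*

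**What the plan says.** All of the following concerns the 20-woman intervention group, mostly in its own form (Consent Groups, Intervention group consent form).

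- **Timing and place (Q7, When and Where Consent Will Occur).** "Consent for the intervention group will be obtained at the Islamic Center during the scheduled education sessions". The next sentence adds: "Participants will have the opportunity to provide consent before engaging in the educational program".
- **Form of the discussion (Q7, How the Consent Discussion Will Occur).** "A designated research team member, such as the research assistant (RA), will conduct the discussion in a private room at the Islamic Center". In that encounter the woman reviews the form, raises questions and decides. No earlier date is given.
- **Length of the programme.** Q7 on reconfirmation of consent: "Since the intervention group will be participating in a one-day educational program". Study Procedures, Q4: "The session will be offered in a single day and last 1.5 hours". Behavioral Intervention/Task Details, Q1, sets the whole event at three hours.
- **Wait before signing (Q8).** "Having a mandatory wait period for the participant to go home and think before they sign consent /assent". This appears as a selected protection, and the summary table under Consent Process, Q1, repeats it for this group. No length is given.
- **Time to decide (Q10).** "Participants will be given sufficient time (expecting from a week to two weeks) to make a decision regarding their participation in the study". The answer goes on to say that the duration can vary.
- **Earlier contact (Study Procedures, Q4 and Q6).** Women receive a flyer or brochure, are screened and are scheduled. "Eligible participants will be given a telephone contact for enrollment at a more convenient time".

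**The concern.** Q7 and Q8 of one form pull in opposite directions. Staff who follow Q7 literally would explain the study, take the signature and start the education at one event. Staff who follow Q8 literally would send the woman home between the explanation and the signature.

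The safeguard at stake is one the plan chose for itself. The wait is selected under the question on undue influence, in a study where that risk is plausible. The plan counts on the Islamic centers to persuade women to join (Background, Q3), the Imam introduces the research (Risks, Q3), and a woman who completes everything receives $150 for the two surveys plus $50 for the satisfaction survey, $200 in all (Compensation, Q1). The other protections listed in Q9 of the form (information, voluntariness, privacy and contact details) do not give her time away from the mosque before she signs.

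The timing of consent also fixes the earliest moment at which a baseline survey can be given, so the two steps should be ordered together.

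**Working it through.** The plan gives no figure to reproduce. The check is whether the stated rules can hold together.

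**Inputs.** Event length is 3 hours = 180 minutes, of which 90 are education and 45 are survey (Behavioral Intervention/Task Details, Q1). Expected decision time is 7 to 14 days (Q10). The go-home wait is mandatory, with no stated length (Q8). Consent comes before the programme begins (Q7).

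**Time at the event.** 180 − 90 − 45 = 45 minutes remain, and these are assigned to break and lunch. None is assigned to consent discussions.

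**Decision time against event length.** 7 × 24 = 168 hours and 14 × 24 = 336 hours. 168 / 3 = 56 and 336 / 3 = 112, so the expected decision time is 56 to 112 times the whole event. The conflict does not depend on this ratio. A wait at home, however short, cannot fall between a discussion and a signature that both precede the education on the same day.

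**Possible sequences.**

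| Discussion | Signature | Go-home wait (Q8) | Consent before programme (Q7) | Described in the plan? |
|---|---|---|---|---|
| At the session | Same session, before education | Not met | Met | Yes, the plain reading of Q7 |
| At the session | Later, after that day's education | Met | Not met | No |
| At one session | Before a later session | Met | Met, at the later session | No |
| At recruitment or scheduling | At or before the session | Met | Met | No |

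The sequence that the form describes is the one that fails Q8. The two that satisfy both rules are feasible but not written down. Study Procedures, Q6, lists the parts of the consent process (verbal explanation, form, questions) but does not date them relative to the session.

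**A smaller looseness.** Q7 places consent *during* the sessions in one sentence and *before* the programme in the next.

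**The case against.** The strongest reply is that nothing here is impossible. First contact comes before the session: women are approached at Friday prayers and religious holidays, given a brochure, screened and scheduled. Q7 says where consent is obtained, which can be read as the place of signature after an earlier approach. The focus-group consent form describes a private discussion not tied to a session, in words that also cover women joining the education session, and it counts its two-week limit from the first conversation. DocuSign is selected for the intervention group (Q3), so signature need not wait for the event. The intervention is a single education session reviewed under expedited categories.

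Much of this stands. It shows that a compliant sequence is available, and it rules out saying that the rules can never be met. It also rules out treating one to two weeks as a fixed requirement: Q10 states an expectation and allows variation, and only the go-home wait is called mandatory.

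What it does not do is supply the missing sequence. The intervention form's own account puts explanation, review and decision in one encounter and places consent at the session. A brochure and a telephone contact are not a consent discussion, and the general wording in the focus-group form does not override the specific answer in the intervention form. If an earlier discussion is intended, stating it is the correction.

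**Conclusion.** The inconsistency is real and limited. Followed as written, Q7 defeats the go-home wait selected in Q8. The rules are compatible only under an earlier discussion that the plan does not describe. This should be corrected before enrolment, because a wait that was skipped cannot be supplied after signature. It has no effect on sample size or error rates.

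The conclusion assumes that the wait in Q8 is selected, as its display and the Consent Process summary table both indicate, and that the discussion in Q7 is the first one.

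A reader might infer more, and the documents do not support it:

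- **That all 20 women sign after zero days.** This holds only if first discussion and signature both fall on the session day for everyone. Recruitment contact is earlier, and the plan speaks of sessions in the plural, on Saturday and Sunday, so a woman who waits may be able to attend a later one.
- **That a baseline survey has no possible slot.** Consent before the programme leaves room for a survey before the education, and Study Procedures, Q4, has baseline surveys scheduled as a step of their own. The baseline problem comes mainly from the intervention summary in that section, which puts the month 0 survey after the educational material. That is a separate point.
- **That enrolled becomes the same as attended, which would distort retention.** No section defines enrolment as signature at the session. Study Procedures, Q6, links enrolment to a telephone contact and tracks enrolment, attendance and completion separately.

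**What to change.** Reconcile Q7, Q8 and Q10 of the intervention-group consent form with each other and with Study Procedures, Q4 and Q6, so that one sequence is stated:

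1. The consent form is handed over and the discussion held at the recruitment or scheduling contact.
2. The woman goes home. The sponsor states how the wait is defined, since Q8 gives no length and Q10 only an expectation.
3. Signature, on paper or through the DocuSign route already selected, follows the wait and precedes any study procedure.
4. The baseline survey is completed after signature and before the first education section.

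Q7 should then drop the statement that consent is obtained during the sessions. The intervention summary in Study Procedures, Q4, should be aligned with step 4.

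The cost is a wording amendment and a fuller conversation at a contact the research assistant already makes. A few women may be lost between that contact and the session.

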**What Will Be Covered During the Consent Discussion:**

During the consent discussion, participants will be provided with a detailed explanation of the educational program, including the topics covered, session duration, and expected outcomes. The risks and benefits associated with participation will be clearly explained, along with any potential discomfort or adverse effects that may arise from the educational sessions. Additionally, participants will be informed about their rights as research participants, including confidentiality and the voluntary nature of their involvement. They will have the opportunity to ask questions and seek clarifications before providing consent.

**How the Consent Discussion Will Occur:**

The consent discussion will occur in-person, allowing for direct communication between the research team and the participants. A designated research team member, such as the research assistant (RA), will conduct the discussion in a private room at the Islamic Center. The participant will have the opportunity to review the consent form, ask any questions, and discuss any concerns before making an informed decision to participate. The RA will be available to provide explanations and guidance as needed to ensure the participant's understanding of the study and their role in it.

**How Consent Will Be Reconfirmed on an Ongoing Basis:**

Since the intervention group will be participating in a one-day educational program, ongoing reconfirmation of consent is not applicable in this case. However, the research team will ensure that participants are aware of their right to withdraw from the study at any time, even after providing initial consent. Participants will also be provided with contact information to reach out to the research team if they have any questions or concerns during or after the educational program.

**8. \* Select the processes for minimizing any potential perception of undue influence to participate, particularly when there is a pre-existing relationship between the participant and the researcher (e.g. treatment provider/patient, instructor/student, supervisor/employee, etc.):**

- Having a 3rd person (family/friends, another study team member, etc.) present during the consent / assent discussion
- Having an independent advocate (e.g. advocate for decisionally impaired adults, wards) present during the consent / assent discussion
- Removing physical symbols of authority like white coats or police badges
- Sitting down beside the participant instead of standing over them
- If obtaining consent / assent in a clinical setting, letting patients sit instead of lie down (if they are able to)
- Moving to a more neutral location like a conference room
- Obtaining consent / assent after other services/interactions have been completed (e.g. after school or the clinic visit)

**Having a mandatory wait period for the participant to go home and think before they sign consent /assent**

- Sharing the consent / assent discussion between two people (i.e. a clinician might be the best person to explain study procedures and risks, but then they could step out and let a research assistant finish the consent process)
- Other protection(s) not listed here – describe below
- N/A: Requesting Waiver of Consent
- Other

